We will test two different doses and routes of ketamine administration: 0.5mg/kg PO and 0.5mg/kg IM. These doses were selected on the basis of existing data. As a safety precaution, we will use a maximum limit of oral ketamine of 60 mg, given that higher doses have not been evaluated in clinical trial settings in the U.S.

Case series and one published clinical trial of oral ketamine as a treatment of depression in patients with advanced cancer have shown that a daily oral dose of 0.5mg/kg is well-tolerated and briefly improved depression symptoms [55-57]. An ongoing trial of weekly oral ketamine for anxiety in patients with pancreatic ductal adenocarcinoma (PDAC) is using a dose of 0.5mg/kg PO [58]. The bioavailability of oral ketamine is estimated to be 10-17% [59].

Clinical trials investigating the use of intramuscular ketamine for the treatment of depression in palliative populations and the general public have used starting doses ranging from 0.1mg/kg -1.0mg/kg IM [60-62], all of which have been reported to be relatively well-tolerated. The bioavailability of intramuscular ketamine is 93% [63, 64]. Similar or higher doses of ketamine are frequently used in various clinical settings. Many trials of IV ketamine for unipolar depression have used a dose of 0.5mg/kg administered as a slow infusion [65], while one survey of n=98 community clinics administering off-label ketamine for psychiatric conditions uses doses ranging from 0.5-3.0mg/kg IV [66]. A retrospective study of n=420 patients receiving IM ketamine for depression found starting doses ranging from 0.3 - 2.15mg/kg IM, with a median starting dose of 0.55mg/kg IM [67]. A second case series of n = 40 patients utilized a protocol involving a starting dose of ketamine 1.0mg/kg IM, divided into two 0.5m/kg IM doses spaced 15 minutes apart [68]. In a recent systematic review of ketamine in palliative care populations, patients were most commonly started at starting doses of ketamine 0.5mg/kg SC or IV [69]. Another survey of three ketamine clinics (two of which are in the San Francisco Bay Area) provided data on n=253 patients treated with off-label ketamine-assisted psychotherapy using sublingual administration (with a bioavailability of 15-25%) at doses of 25-400 mg, and often in the range of 200-250 mg [70]. Finally, in an FDA-related abuse liability study published in 2011, 100 mg of oral ketamine was used as a control drug for the serotonin 2C receptor agonist lorcaserin [71].

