the study team will read the questions to the potential participant, and the potential participant's answers will be recorded by the study team. If the score is ≥10/32, the study team will talk to the participant about joining the study. The data from the phone screen will only be used for screening and will not be used as research results. The second DS-II measurement will be given to the participant in person after they have signed the informed consent form on the day of enrollment (i.e. baseline, between Day -28 and -7). The DS-II questions will be administered to the patient either on paper or electronically with a tablet (using REDCap). Following best practices with patient-reported outcomes [73], participants will fill out the second DS-II without clinician or study staff involvement. In the event that a participant has a question about how to fill out the questionnaire, study staff will be trained only to read the instructions printed at the top of the measure or to assist the participant with reading a particular item, but staff will say nothing beyond reading the wording on the instrument itself. The DS-II will be scored by summing the responses to all 16 items to generate a total score. Participants must score a 10 or higher in order to be eligible for the study.

If the participant meets all of the eligibility criteria, they will be randomized 1:1 on Day 0 to one of two cohorts (0.5 mg/kg of ketamine PO or 0.5 mg/kg of ketamine IM). The study is double-blinded, meaning neither the study participants nor the study investigators will know which dose of ketamine each participant is receiving. Participants randomized to receive ketamine 0.5 mg/kg PO will receive an equivalent quantity of normal saline (placebo) via an intramuscular injection after ingesting oral ketamine, and those who are randomized to receive ketamine 0.5 mg/kg IM will receive their IM injection after ingesting an equivalent quantity of normal saline (placebo) orally. Orally administered ketamine and normal saline (placebo) will be mixed in cranberry juice immediately prior to being administered to the patient.

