3.8 Randomization Procedures

A total of 12 patients will be randomized on Day 0 at a 1:1 ratio to receive either 0.5 mg/kg of oral ketamine, or 0.5 mg/kg of IM ketamine. Randomization will be in block sizes of 4.

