The participant will be randomized to ingest liquid ketamine 0.5mg/kg vs. an equivalent mL quantity of normal saline (placebo) mixed with cranberry juice (prepared by unblinded study staff) in a medication administration room located next door to the treatment room. At 10 minutes following oral ingestion of cranberry juice, while sitting in a wheelchair in the medication administration room, all participants will be administered an intramuscular injection (also prepared by unblinded study staff). The injection will be administered either by an RN, NP, or MD/DO involved in the study. Participants who received oral ketamine 0.5mg/kg will be administered normal saline via IM injection while those who received normal saline (placebo) in cranberry juice will receive ketamine 0.5 mg/kg IM. Following this injection, the participant (still in a wheelchair) will be rolled into the treatment room located across the hall from the medication administration room, where they will be supported by the therapy facilitators in transferring from the wheelchair to the couch and instructed to lie down wearing eyeshades and listening to a preselected music playlist via headphones or speakers. The participant will be instructed to focus their attention internally and to attempt to interact minimally with the two facilitators present in the room throughout the drug session. The facilitators will be as nondirective as possible in their interactions with the participant. In the event of a psychologically challenging experience such as significant anxiety or confusion, the facilitators will provide verbal reassurance and, when consented to prior to the session, supportive touch (e.g., brief handholding or hand-on-shoulder). Participants will have been instructed in the preparatory therapy session to notify the study therapists if during the treatment they feel anxiety or fear.

Facilitators will work in dyads (one Lead Facilitator and one Assistant Facilitator) and have licensure or clinical experience according to the following requirements, which the FDA has used for prior studies of medication-assisted talk therapy:

Lead Facilitator: Licensed to provide healthcare with professional training and clinical experience in psychotherapy. They must be licensed to practice independently. Acceptable professional credentials are limited to the following: clinical or counseling psychologist (PhD or PsyD), psychiatrist or other

Pilot Study - Ketamine Page 25 of 55

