5.1 Dosage and Administration

Treatment with ketamine will be administered on an outpatient basis, on Day 0/Visit 4.

This session will last about 4-5 hours. Participants will arrive to the Neurosciences Clinical Research Unit (NCRU) of the Sandler Building at UCSF Mission Bay, where they will be oriented to the treatment room for this study, which will contain a couch or bed for the participant to lie on in a private setting. Participants will hand over their shoes, keys, wallet, and phone to the study clinicians for safekeeping; these will all be returned to the participant upon completion of the treatment session. The session will be audio and video recorded for subsequent behavioral analysis and rating of clinician adherence to the trial protocol. Participants will have the option of requesting that the recording be paused momentarily if they wish to discuss matters that are too personal to be recorded. There will be an onsite study physician (MD or DO) with experience in the management of psychiatric emergencies and experience or certification in the management of cardiovascular emergencies. administration, and the medication visit will be paid for by the study and will not be billed to participants or their insurance. The participant will be randomized to ingest liquid ketamine vs. an equivalent mL quantity of normal saline (placebo) mixed with cranberry juice (prepared by unblinded study staff) and then be administered an intramuscular injection (prepared by unblinded study staff) 10 minutes later. Participants who received oral ketamine 0.5mg/kg will be administered normal saline via IM injection while those who received normal saline (placebo) in cranberry juice will receive ketamine 0.5 mg/kg IM. Following this injection, participants will be moved from the medication administration room into the treatment room via wheelchair, transferred to the couch, and instructed to close their eyes while wearing eyeshades and listening to a preselected music playlist via headphones and speakers. The participant will be instructed to focus their attention internally and to attempt to interact minimally with the two facilitators, who will be present in the room throughout the drug session but will be as nondirective as possible in their interactions with the participant. In the event of a psychologically challenging experience such as significant anxiety or confusion, the facilitators will provide verbal reassurance and, when consented to prior to the session, supportive touch (e.g., brief handholding or hand-on-shoulder). Participants will have been instructed in the preparatory therapy session to notify the study therapists if during the treatment they feel anxiety or fear.

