
Ketamine preparation

On Day 0, an unblinded preparer will draw up a 0.5 mg/kg dose of liquid ketamine solution into a syringe. They will also draw up an equivalent mL quantity of normal saline in an identical syringe. Using a computer-generated randomization scheme, they will then mix either the liquid ketamine or normal saline solution into a cup of cranberry juice. This drug-cranberry juice admixture and the second syringe (containing either ketamine or saline solution) will then be handed to a blinded study therapist, who will administer the medications to the study participant.

Investigational Product	Premedication; precautions	Dose	Route	Schedule
Ketamine	N/A	0.5 mg/kg	Oral or Intramuscular	One dose, on Day 0/Visit 4

Pilot Study - Ketamine Page 27 of 55

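### The 60 mg oral ketamine maximum in Section 1.3 is not carried into the dosing instructions in Section 5.1, so an oral-arm participant above 120 kg dosed from 5.1 would exceed it

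*Combined protocol and SAP*

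**What the plan says.** Section 1.3, under the rationale for dose selection, commits to an absolute ceiling on the oral dose: "we will use a maximum limit of oral ketamine of 60 mg". The reason given is that larger oral doses have not been studied in US trials.

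The sections that govern dosing do not repeat it:

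- Section 3.8 randomizes participants "to receive either 0.5 mg/kg of oral ketamine, or 0.5 mg/kg of IM ketamine".
- Section 3.1 states the oral dose the same way and adds the matching injection: "Participants randomized to receive ketamine 0.5 mg/kg PO will receive an equivalent quantity of normal saline (placebo) via an intramuscular injection".
- Section 5 and the narrative of Section 5.1 again give oral ketamine at 0.5 mg/kg, for example "Participants who received oral ketamine 0.5mg/kg will be administered normal saline via IM injection".
- The preparation text in Section 5.1 says that "an unblinded preparer will draw up a 0.5 mg/kg dose of liquid ketamine solution into a syringe". The preparer then fills an identical syringe with the same volume of saline. The allocation is used only after that: "Using a computer-generated randomization scheme, they will then mix either the liquid ketamine or normal saline solution into a cup of cranberry juice". The juice and the remaining syringe "will then be handed to a blinded study therapist, who will administer the medications to the study participant".
- The dose table in Section 5.1 has one line for both routes, 0.5 mg/kg, with nothing entered as a precaution.

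Section 3.3 sets no limit on weight. The calendar in Section 6.1 records weight at Visit 1 but does not link it to a dose check. Section 4.2 says the institution's investigational drug service is not engaged in the trial, so no second check by that service is described.

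**The concern.** The person preparing the dose works from Section 5.1, not from the background rationale. Section 5.1 gives a complete recipe (dose per kilogram, matching saline, allocation, mixing) that contains no ceiling. For a heavy participant allocated to oral ketamine, following it exactly produces a dose that Section 1.3 rules out. The protocol would then have been both followed and breached, in respect of a limit it calls a safety precaution.

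There is a second, practical reason to write the step down. A preparer who remembers the ceiling has to decide when to apply it. If it is applied when the syringes are filled, before the allocation is used, an IM participant's dose is capped as well, although the maximum is written for oral ketamine only.

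**Working it through.** The 60 mg is a chosen limit, not a derived figure, so there is nothing to reproduce. The check is a comparison of the dosing text plus simple arithmetic.

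**Inputs.** Oral maximum 60 mg (Section 1.3). Dose 0.5 mg/kg (Sections 3.1, 3.8, 5, 5.1). Bioavailability 10–17% oral and 93% IM (Section 1.3). Preferred concentration 50 mg/mL (Section 4.1.1). Six participants per arm (Sample Size row of the opening summary).

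**Step 1: weight at which the limit binds.** 60 mg ÷ 0.5 mg/kg = 120 kg. At or below 120 kg nothing changes; the illustrative 70 kg person in Section 1.3 would receive 35 mg.

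**Step 2: excess over the limit if 5.1 is followed as written.** Written dose = 0.5 × weight. Excess = written dose − 60. Systemic excess = excess × 0.10 to excess × 0.17.

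| Weight | Written oral dose | Excess | Excess as % of 60 mg | Systemic excess |
|---|---|---|---|---|
| 130 kg | 65 mg | 5 mg | 8.3% | 0.5–0.85 mg |
| 150 kg | 75 mg | 15 mg | 25% | 1.5–2.55 mg |

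**Step 3: scale against the other arm.** At 150 kg, uncapped oral gives at most 75 × 0.17 = 12.75 mg systemic, and capped oral at most 60 × 0.17 = 10.2 mg. IM gives 75 × 0.93 = 69.75 mg by design.

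**Step 4: how often the limit could matter.** The documents give no participant weights, so this rests entirely on assumptions. With p the share of participants above 120 kg, the chance that at least one of six oral-arm participants is affected is 1 − (1 − p)^6.

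| Assumption | p | Chance of at least one of 6 |
|---|---|---|
| Normal weights, mean 70, SD 15 | 0.043% | 0.3% |
| Normal weights, mean 80, SD 18 | 1.3% | 7.6% |
| Share set directly | 1% | 5.9% |
| Share set directly | 2% | 11.4% |
| Share set directly | 5% | 26.5% |
| Share set directly | 10% | 46.9% |

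Even at the top of this range it is more likely than not that nobody is affected.

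**Step 5: what the written order implies for the injection.** Take 130 kg and 50 mg/mL. Section 5.1 has the preparer fill both syringes first: 65 mg ketamine = 1.3 mL, saline = 1.3 mL.

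- Cap applied at mixing: in the oral arm 1.2 mL (60 mg) of ketamine goes into the juice and the saline syringe for injection holds 1.3 mL. In the IM arm the ketamine syringe for injection holds 1.3 mL. Injection volumes are equal.
- Cap applied at filling: both syringes hold 1.2 mL whichever route follows. Injection volumes are again equal, but an IM participant receives 60/130 = 0.46 mg/kg, which the protocol does not intend.

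**The case against.** The best reply is that nothing is contradicted. Section 1.3 is part of the same protocol and is worded as a commitment. A dose per kilogram and an absolute maximum are normally read together, and no section says the oral dose is uncapped. The unblinded preparer knows the route at mixing and could apply the limit there. It can be added that the consequences are trivial: no endpoint or estimate changes, the excess exposure is small beside what the IM arm receives, and Section 1.3 itself cites a study that used 100 mg orally.

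Much of this stands, and it is why the point is minor. It does not remove the point. The text that staff dose from gives a number the protocol elsewhere forbids, and no step tells anyone to check.

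Three stronger readings are tempting, and the documents do not support them:

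- *The current text threatens the blind.* A reader might infer that a capped oral dose would be paired with a smaller saline injection, so that the blinded therapist could recognize the arm. Section 3.1 alone leaves the matching quantity open, but the order in 5.1 settles it. The saline is matched to the ketamine drawn before the allocation is used, so injection volumes are equal across arms wherever the cap is applied. Unequal volumes would need a departure from that order.
- *Section 9.2.1 would drop a capped participant.* The analysis population is described as those dosed at 0.5 mg/kg, and a capped participant receives 0.46 mg/kg at 130 kg or 0.40 mg/kg at 150 kg. But the definition covers everyone who received a dose of ketamine on Day 0. The figure is most naturally read as naming the regimen, and reading it as an exclusion is strained.
- *The omission is a toxicity risk.* The exposure figures do not bear this out.

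**Conclusion.** The inconsistency is real and minor. The threshold of 120 kg and the doses above it follow directly from the protocol's own numbers and need no assumption; the systemic figures also use the bioavailabilities that the protocol quotes. How often it would matter cannot be established from the documents and depends on assumed weights; most likely no participant is affected. What is at stake is an avoidable breach of a declared safety limit, not patient harm, the blind or any analysis. It is worth correcting because the limit is the sponsor's own and the correction is a few lines.

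**What to change.** In the preparation text and dose table of Section 5.1, state the dose by route: *oral: 0.5 mg/kg, maximum 60 mg; IM: 0.5 mg/kg*.

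Keep the existing draw-up order and add one step after the allocation is consulted. If it is oral and the drawn ketamine exceeds 60 mg, the unblinded preparer adds only 60 mg to the juice (1.2 mL at 50 mg/mL), discards the rest and records it in the usage log required by Section 4.2. The saline syringe already drawn stays at the uncapped 0.5 mg/kg volume (1.3 mL at 130 kg and 50 mg/mL). This leaves the IM dose uncapped and keeps injection volumes equal in the two arms. The small difference in oral volume goes into a cup of juice.

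Optional in the same amendment: reword Section 9.2.1 to all participants who received any study ketamine on Day 0.

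Cost: under Section 9.6, a change after IRB approval is a protocol amendment that must be signed by the investigator and approved by the protocol review committee and the IRB. The wording is short. Sample size, visits, IM dose and analyses do not change.

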2.1 Hypothesis

We hypothesize that K-MaP therapy is safe and feasible for administration to patients with advanced GI cancers with moderate-to-severe demoralization. In addition, we hypothesize that stage 3 and 4 GI cancer patients will tolerate K-MaP therapy, and patient experiences during K-MaP therapy may result in improvements from randomization in measures of psychosocial distress, pain, opioid analgesic use, and interoceptive awareness.

2.2 Primary Objective and Endpoint(s)

Primary Objective	Endpoint(s)	Time Frame		
To assess the feasibility of Meaning and Purpose therapy combined with ketamine (K-MaP) in	Rate of recruitment (i.e., proportion enrolled and fully eligible vs screened participants).	From time of screening to enrollment.		
demoralized patients with advanced GI cancers.	2. Proportion of enrolled participants completing (i) K-MaP intervention (receiving ketamine, all four Meaning and Purpose therapy sessions) and (ii) all DS-II assessments, by arm.	2. From Day -28 to Day 14 (about 28 days).		
	Qualitative review of clinician fidelity to manualized K-MaP intervention.	3. From Day -14 to Day 14 (about 28 days).		
	4. Qualitative feedback on acceptability to participants of the intervention and assessments (20-minute interview with participants upon study termination), by arm.	4. On Day 35.		

2.3 Secondary Objectives and Endpoints

Secondary Objective	Endpoint(s)	Time Frame

Pilot Study - Ketamine Page 15 of 55

1.	To characterize the preliminary safety and tolerability of K-MaP in patients with stage 3 and 4 GI cancers.	 Adverse events (AEs), Unexpected AEs, and Serious AEs, by CTCAE (v.5.0). Vital signs (heart rate and blood pressure) Patient-reported outcome: challenging experiences (CEQ) 	 Day -28 through Day 35. Day 0 (multiple time points on day of ketamine administratio n). Day 0, 3-4 hours after ketamine administratio n.
2.	To assess the magnitude and durability of improvement from randomization in psychosocial distress.	 Clinician-rated outcomes: Global clinical impression of severity(CGI-S), Demoralization (DI), Mood symptoms (GRID-HAMD-6). Patient-reported outcomes: Demoralization (DS-II), Depression (PHQ9), Anxiety (GAD7), Quality of Life (FACIT-PaI-14). 	From Day -28 to Day 35.
3.	To assess the magnitude and durability of improvement from randomization in pain.	Patient-reported outcome: pain (BPI-SF)	From Day -28 to Day 35.
4.	To assess the magnitude of change from randomization in opioid analgesic use.	Patient-reported outcome: Opioid use (<24hr morphine milligram equivalence [MME])	From Day -28 to Day 35.
5.	To assess the magnitude of change from randomization in interoceptive awareness.	Patient-reported outcome: interoceptive awareness (MAIA-2)	From Day 0 to Day 7

Pilot Study - Ketamine Page 16 of 55

2.4 Exploratory (Correlative) Objectives

Exploratory Objective	Endpoint(s)	Time Frame		
To assess how the participants' subjective experiences with ketamine may be related to clinical outcomes.	Patient-reported outcome: Subjective reports of participants' ketamine experiences on Day 0 will be transcribed, inductively coded and analyzed to identify phenomenological content that may be related to clinical outcomes Patient-reported outcome: Challenging and mystical experience questionnaire (CEQ and MEQ) scores correlated with changes in reported measures of demoralization (DS-II), pain (BPI-SF), and	Day 0 From Day -28 to 35.		
	opioid use (MME).			
2. To assess how the participants' changes in measures of cardiac interoception following receipt of ketamine may be related to subjective experiences with ketamine and clinical outcomes.	Patient-reported outcome: Changes in scores on a heartbeat detection task (HBD) conducted before and after ketamine correlated with scores on the mystical experience questionnaire (MEQ) as well as changes in reported measures of interoceptive awareness (MAIA-2), demoralization (DS-II), pain (BPI-SF), and opioid use (MME).	From Day -28 to 35.		

3 Study Design

3.1 Characteristics

This is a parallel-arm, double-blind, randomized controlled pilot trial (N=12) of two different dose levels of ketamine administered as a single dose, in combination with 4 sessions of Meaning and Purpose therapy (MaP) for stage 3 and 4 GI cancer patients (including those with primary pancreatic, gastroesophageal, hepatocellular, biliary, and colorectal malignancies) experiencing moderate-to-severe demoralization.

Demoralization is a clinically significant and measurable form of existential distress characterized by poor coping and a sense of helplessness, hopelessness, and a loss of meaning and purpose in life [2, 3]. Demoralization will be measured by Demoralization Scale-II (DS-II), a validated measure [4]. The scale includes 16 items, and a total score of 10 or higher indicates moderate-to-severe demoralization.

Participants will be administered 2 sessions of MaP before drug administration, and 2 sessions after drug administration. The combination of ketamine and Meaning and Purpose therapy will be referred to as K-MaP.

Adult GI oncology patients at HDFCCC and other Bay Area medical centers will be referred by their clinical teams. Referred patients must demonstrate clinically significant and stable demoralization as measured by DS-II ≥10/32 two times ≥7 days apart (both during screening) to be eligible for the study. The first measurement of the DS-II scale will occur over the phone. After a verbal waiver of consent,

Pilot Study - Ketamine Page 17 of 55

the study team will read the questions to the potential participant, and the potential participant's answers will be recorded by the study team. If the score is ≥10/32, the study team will talk to the participant about joining the study. The data from the phone screen will only be used for screening and will not be used as research results. The second DS-II measurement will be given to the participant in person after they have signed the informed consent form on the day of enrollment (i.e. baseline, between Day -28 and -7). The DS-II questions will be administered to the patient either on paper or electronically with a tablet (using REDCap). Following best practices with patient-reported outcomes [73], participants will fill out the second DS-II without clinician or study staff involvement. In the event that a participant has a question about how to fill out the questionnaire, study staff will be trained only to read the instructions printed at the top of the measure or to assist the participant with reading a particular item, but staff will say nothing beyond reading the wording on the instrument itself. The DS-II will be scored by summing the responses to all 16 items to generate a total score. Participants must score a 10 or higher in order to be eligible for the study.

If the participant meets all of the eligibility criteria, they will be randomized 1:1 on Day 0 to one of two cohorts (0.5 mg/kg of ketamine PO or 0.5 mg/kg of ketamine IM). The study is double-blinded, meaning neither the study participants nor the study investigators will know which dose of ketamine each participant is receiving. Participants randomized to receive ketamine 0.5 mg/kg PO will receive an equivalent quantity of normal saline (placebo) via an intramuscular injection after ingesting oral ketamine, and those who are randomized to receive ketamine 0.5 mg/kg IM will receive their IM injection after ingesting an equivalent quantity of normal saline (placebo) orally. Orally administered ketamine and normal saline (placebo) will be mixed in cranberry juice immediately prior to being administered to the patient.

K-MaP will consist of 4 sessions of Meaning and Purpose (MaP) therapy and a single dose of ketamine on Day 0. Two MaP sessions will occur prior to ketamine therapy at least 2 days apart, the 1st session between Days -13 and -4, and the second session between Days -12 and -1. The two sessions of MaP after ketamine administration will occur on Days 3 (+/- 2 days) and 11 (+/- 2 days). All five intervention visits will be booked at the participant's baseline visit (see Study Schema).

